**Amendment 1 protocol 10 May 2017**

**Original Protocol, 24 Jul 2015**

**6. Milestones**

Milestone	Planned date
Start of data collection	November 2015
End of data collection	1° Quarter 2021
Final report of study results	4° Quarter 2021

**7. Rationale and Background**

Two anti-EGFR monoclonal antibodies are currently available for the upfront treatment of RAS wt mCRC patients: the chimeric IgG1 cetuximab, in combination with both FOLFOX or FOLFIRI, and the fully human IgG2 panitumumab, in combination with FOLFOX or FOLFIRI.

Although anti-EGFR monoclonal antibodies have a more targeted and specific action on tumour cells than conventional cytotoxic chemotherapy drugs, they are not devoid of side effects. In particular, cutaneous effects, tightly connected to the mechanism of action of anti-EGFR monoclonal antibodies, are frequent (50-90%) and sometimes severe. They mainly include acneiform papulopustular reactions and, more rarely, eczematiform rashes or paronychia. An active and early management of these adverse events is crucial in order to improve patients' quality of life and to guarantee an adequate adherence to the treatment. Clinical practice guidelines for the prevention and treatment of anti-EGFR-related dermatologic effects have been developed thanks to the joint effort of experts in dermatology, medical and supportive oncology.

Approved

While a robust amount of evidences has been collected with regard to the safety profile of FOLFOX/FOLFIRI plus an anti-EGFR in clinical trials conducted according to Good Clinical Practice procedures, information from the “real-life” setting about the incidence of most common adverse events and their impact on patients’ quality of life is still lacking.

The use of these combinations, especially with regard to the oxaliplatin-based chemotherapy backbone, has been recently implemented in the daily Italian clinical practice. In this observational study the safety profile, in terms of incidence and grade, but also pattern of occurrence and management, of adverse events will be accurately described, as well as treatments’ duration and modifications. The study will provide useful insights into the current management of patients treated with FOLFOX/FOLFIRI plus panitumumab or FOLFOX/FOLFIRI plus cetuximab in the Italian clinical practice. These results will probably help clinicians to become more and more confident with respect to the adoption of these combinations in their **routinely** activity

#### 7.1 Diseases and Therapeutic Area

Different options are currently available as upfront choices for the systemic treatment of metastatic colorectal cancer patients. In the last years different phase III trials investigated the addition of a drug targeting the Epidermal Growth Factor Receptor (anti- EGFR) to a first-line chemotherapy doublet, leading to the approval of two anti-EGFR monoclonal antibodies: the chimeric human-murine IgG1 cetuximab and the fully human IgG2 panitumumab.

The prospective and *post-hoc* analyses of randomized trials of first-line chemotherapy with or without an anti-EGFR monoclonal antibody, show that patients bearing a mutation in *KRAS* codon 12 or 13 do not benefit from the addition of the anti-EGFR to the upfront chemotherapy doublet, so that the use of both cetuximab and panitumumab has been restricted to *KRAS* wild-type patients. More recently, a pre-specified analysis of results of the PRIME trial showed for the first time that also patients bearing a mutation in some hotspots of *KRAS* (other than codon 12 and 13) and *NRAS* genes (ie, codon 12, 13, 59, 61, 117 and 146) do not achieve benefit from the addition of cetuximab or panitumumab to first-line chemotherapy. A potential detrimental effect of adding anti-EGFRs to first-line FOLFOX was also suggested in mutated patients. On the other hand, the efficacy of anti-EGFR monoclonal antibodies was optimized in patients not bearing any mutation in *KRAS* or *NRAS* codon 12, 13, 59, 61, 117 and 146, defined as *RAS* wild-type patients. Based on these results, the European Medicines Agency further

restricted the use of both panitumumab and cetuximab to this subgroup of patients. In March 2015, the European Medicines Agency approved the extension of indication for Panitumumab FOLFIRI in 1st line. The new indication was implemented by Italian Medicines Agency on 24 February 2017.

Therefore doublet plus panitumumab or cetuximab are valuable options for the upfront treatment of *RAS* wild-type mCRC patients.

Results from a phase II (PEAK) and a phase III (FIRE-3) randomized trials comparing a chemotherapy doublet plus an anti-EGFR with a chemotherapy doublet plus the anti- Vascular Endothelial Growth Factor bevacizumab suggest that the upfront use of the anti-EGFR may be beneficial for *RAS* wild-type patients in terms of overall survival, thus further supporting the adoption of these regimens as first-line choices. These findings have not been confirmed by another phase III trial (CALGB80405) showing no significant differences between a chemotherapy doublet (mainly FOLFOX) plus cetuximab or bevacizumab in terms of OS. A higher response rate was however reported in the chemotherapy plus cetuximab group. Based on these results both chemotherapy plus an anti-EGFR or chemotherapy plus bevacizumab are valid options as upfront treatment for mCRC patients. The choice will be mainly based, on a case-by-case basis, on the treatment's objective and on patients' expectations. To this regard, the impact of the treatment on patients' quality of life, that is tightly connected to the management of occurring adverse events, as well as physicians' confidence with these regimens will be of crucial importance.

In Italy two anti-EGFR MAbs are currently approved for the treatment of adult patients with wild-type *RAS* metastatic colorectal cancer.

Panitumumab is indicated for the treatment of adult patients with wild-type *RAS* metastatic colorectal cancer:

- in first-line in combination with FOLFOX or FOLFIRI;
- in second-line in combination with FOLFIRI for patients who have received first- line fluoropyrimidine-based chemotherapy (excluding irinotecan);
- as monotherapy after failure of fluoropyrimidine, oxaliplatin, and irinotecan containing chemotherapy regimens.

Approved

Cetuximab is indicated for the treatment of patients with epidermal growth factor receptor (EGFR)-expressing, *RAS* wild-type metastatic colorectal cancer:

in combination with irinotecan-based chemotherapy;

in first-line in combination with FOLFOX;

as a single agent in patients who have failed oxaliplatin- and irinotecan-based therapy and who are intolerant to irinotecan.

Dermatologic adverse events of any grade are observed in more than 90% of patients treated with panitumumab and appropriate dose reductions and delays are suggested in the case of skin symptoms  $\geq$  G3 according to the NCI CTCAE classification.

## 7.2 Rationale

A few data are currently available about the impact of upfront FOLFOX/FOLFIRI plus anti-EGFR MAb on patients' quality of life. These patients' reported outcome is extremely relevant by a clinical point of view when choosing every treatment with a palliative intent, but especially when two or more options are available and no clear advantage by one of them has been demonstrated. Since dermatological toxicities are adverse events of special interest when using anti-EGFR monoclonal antibodies, a specific tool to investigate the impact of skin alterations on patients' quality of life will be adopted. The quality of life during the treatment is certainly influenced also by the incidence and the management of adverse events. No data are currently available about the management of anti-EGFR-derived skin toxicity in Italian clinical practice.

## 7.3 Statistical Inference (Estimation or Hypothesis[es])

No formal hypothesis will be tested in this study. Statistical analyses will be descriptive only. No statistical inference is planned.

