## 9. Research Methods

### 9.1 Study Design

This is a national, multicentric, prospective, observational trial. The decision to prescribe FOLFOX or FOLFIRI plus panitumumab or FOLFOX or FOLFIRI plus cetuximab must have been freely taken by the clinician prior to the study entry for each patient included. Each physician will see his/her patients within the context of routine visits, without any special visit being organized for the purposes of the study. Therefore, the doctor-patient relationship and patient follow-up are not modified. Physicians are totally free to decide on their patients' therapeutic management.

EORTC QLQ-C30 and DLQI questionnaires will be completed by the patients at baseline (Day 1 of Cycle 1), at the first day of every other cycle (every 2 weeks) thereafter, and at "End of Study Visit" (within 28 days from the end of treatment with anti-EGFR or withdrawal from study for any reason).

Before every cycle, adverse events will be recorded and graded according to NCI CTCAE Version 4.0. Treatment's modifications in terms of cycles' delay, dose reductions or drugs' interruptions will be recorded. Concomitant approaches to prevent or treat dermatological toxicities during the treatment will be registered.

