**Table 1. FLOW-chart**

	Screening	Baseline (Day 1 Cycle 1)	Study visit (repetible visit) Cycle 1-cycle N	End Of Study Visit
ICF signature	x			
Inclusion and exclusion criteria	x			
Personal data	x			
Medical History	x			
Physical examination	x	x	x	x
Disease Information	x			
Prevention of cutaneous toxicity		x	x	
Mg levels		x	x	x
Concomitant Medications		x	x	x
AE/SAE		x	x	x
Skin toxicity and Skin Management			x	x
Treatment administered		x	x	
(DLQI) questionnaire		x	x	x
EORTC QLQ-C30		x	x	x

Approved

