#### **9.7.2.1 General Considerations**

All recorded parameters will be described: absolute frequency and percentage will be calculated for qualitative variables, while mean, standard deviation, median, first and third quartile will be used to summarize quantitative variables.

The population will be analyzed totally and stratified for treatment (FOLFOX plus panitumumab and FOLFOX plus cetuximab).

The level of significance will be set to  $p < 0.05$ . No interim analyses are planned for this study.

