#### **9.7.2.4 Analysis of the Primary, Secondary, and Exploratory Endpoint(s)**

To reach the primary endpoint ("To assess the impact of the treatment with FOLFOX or FOLFIRI plus anti-EGFR MAbs on patients' health related quality of life"), comparison between the QoL scores (total and partials) at different times will be done and

differences in mean from basal and follow-up times will be tested with T-test (Student T-test) paired data.

EORTC-QLQ C30 score will be calculated in the total population and also in the two subgroups: FOLFOX/FOLFIRI plus panitumumab and FOLFOX/FOLFIRI plus cetuximab.

Differences in mean between the two subpopulation will be tested at different times with T-test.

- To investigate the impact of dermatological adverse events during the treatment with FOLFOX or FOLFIRI plus anti-EGFR MABs on patients' skin satisfaction will be calculated the Dermatology Life Quality Index (DLQI) score.

Differences in mean between the two subpopulation will be tested at different times with T-test.

- To assess the tolerability of administered treatments, Tolerability and compliance to treatments will be described. Their effect on QoL will be evaluated with a multivariate analysis (Anova).
- To describe the adherence to the treatment **with antiEGFR** in terms of dose delays, dose reductions, number of administered cycles, average relative dose intensity of every drug, all these parameters will be described and the single values observed will be compared with the values reported previously, to determine variations .
- Every adverse event occurred will be described with particular attention to dermatologic ones: description, severity and management of the event will be illustrated. Correlation with number of event and treatments (FOLFOX/FOLFIRI plus panitumumab and FOLFOX/FOLFIRI plus cetuximab) will be verify with a multivariate analysis (Anova)
- Will be verified the presence of preemptive treatment of skin toxicities, and events of skin toxicities . The correlation between events of skin toxicities, QoL and presence of preemptive treatment will be tested with a multivariate analysis (Logistic)

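### Section 7.3 rules out inference, yet the primary QLQ-C30 analysis is a set of t-tests at p<0.05 with no primary scale, primary time or multiplicity rule

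*Combined protocol and SAP*

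**What the plan says.** Section 7.3 leaves no room for testing: "No formal hypothesis will be tested in this study. Statistical analyses will be descriptive only. No statistical inference is planned". The hypothesis entry in the abstract (Section 4) also says that no formal hypothesis is tested.

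The analysis sections say something else. Section 9.7.2.1 contains the sentence beginning "The level of significance will be set to", with p<0.05 as the level, and the abstract repeats it. For the primary endpoint, Section 9.7.2.4 says that a "comparison between the QoL scores (total and partials) at different times will be done" and that "differences in mean from basal and follow-up times will be tested with T-test (Student T-test) paired data". It goes on: "EORTC-QLQ C30 score will be calculated in the total population and also in the two subgroups", meaning the panitumumab and cetuximab groups. It then orders t-tests between those groups at different times, again for the DLQI, and adds Anova and logistic models.

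The primary objective in Section 8.1 names the questionnaire but no scale and no time. Section 9.3.2 lists the QLQ-C30 scales and items and defines no total score.

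On timing, Section 9.1 has the questionnaires completed at baseline, "at the first day of every other cycle (every 2 weeks) thereafter", and at the End of Study Visit. Table 1 puts them in the column "Study visit (repetible visit) Cycle 1-cycle N", and Section 9.3 lists them at each repeatable study visit.

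**The concern.** Sections 7.3 and 9.7.2.4 cannot both be followed. A purely descriptive study needs no significance level. A study that tests its primary endpoint at 0.05 needs a defined endpoint and some control over how many tests are made.

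As written, the primary endpoint is a family of tests of unknown size. The plan does not settle which scores count, what the total is, which times are compared, or how many there are. Results will be labelled significant with no error rate behind the label. Section 7.2 presents quality of life as important when choosing between treatments with no clear winner, so such labels, including those on non-randomised drug comparisons, may be given weight they cannot carry.

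**Working it through.** **The plan's own figure.** Section 9.5 gives 300 patients, about 50% of whom complete the questionnaires throughout: 300 x 0.50 = 150. This is correct, but it is a feasibility figure. The plan states no power, number of tests or familywise error rate, so there is none to reproduce.

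**Inputs.**
- Scores, from Section 9.3.2: 5 functional scales + 3 symptom scales + 1 global scale + 4 single symptoms + 1 financial item = 14.
- Level: 0.05 per test, from Section 9.7.2.1, with no adjustment.
- Last possible cycle: 56, from the End of Study Visit text in Section 9.3.
- Schedule: two readings of Section 9.1, alternate cycles or every cycle.
- Assumptions not in the documents: every score is tested at every post-baseline assessment; no mean truly differs; and 12 cycles serve as a shorter case, because the documents give no expected treatment length.

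**Number of times.** To cycle 12: cycles 3, 5, 7, 9, 11 plus End of Study = 6, or cycles 2 to 12 plus End of Study = 12. To cycle 56: cycles 3 to 55 in steps of two plus End of Study = 28, or cycles 2 to 56 plus End of Study = 56.

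**Formula.** Tests = 14 x times. Expected chance results = 0.05 x tests, whatever the correlation between tests. One between-drug test per score and time doubles both.

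| Case | Times | Paired tests | Expected by chance | With between-drug tests | Expected by chance |
|---|---|---|---|---|---|
| 12 cycles, alternate | 6 | 84 | 4.2 | 168 | 8.4 |
| 12 cycles, every | 12 | 168 | 8.4 | 336 | 16.8 |
| 56 cycles, alternate | 28 | 392 | 19.6 | 784 | 39.2 |
| 56 cycles, every | 56 | 784 | 39.2 | 1,568 | 78.4 |

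The DLQI tests and the Anova and logistic models are left out. If the undefined total is a fifteenth score, each count rises by 1/14, about 7%.

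**At least one chance result.** With independent tests, 1 - 0.95^84 = 98.7%. Scales and visits are correlated, which leaves the mean unchanged but widens the spread. In a simulation with assumed correlations of 0.4 between scales and 0.5 between times, 84 tests gave a mean of 4.2, a median of 3, a 5th to 95th percentile range of 0 to 12, and at least one chance result in 90% of runs. For 784 tests the mean was 39, the median 30 and the range 11 to 99.

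**Effect of true change.** Only comparisons with no true difference can yield a chance finding. If half of them had a real difference (an illustration), the paired counts would halve: 2.1 to 4.2 over 12 cycles, and 9.8 to 19.6 to cycle 56.

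**After a fix that keeps one test.** One scale at one time carries a 5% error. All 14 scores at a single time, unadjusted, would still give 14 x 0.05 = 0.7 expected, and 1 - 0.95^14 = 51% for at least one if independent.

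**The case against.** The best defence is that this is an observational study sized on feasibility, with no power claim, so its p-values are descriptive aids. That softens the consequence but leaves the contradiction. Section 9.7.2.4 ties the tests to the primary endpoint, 9.7.2.1 gives them a threshold, and no section limits how they are read.

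Several stronger readings are tempting and should not be made.

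- A reader might infer that the plan tests every scale at every visit. It does not say so. It speaks of total and partial scores at different times, and the full grid is only a natural reading.
- A reader might infer that dozens of false positives are to be expected. In the paired family that needs testing far beyond 12 cycles, and cycle 56 is a trigger for the End of Study Visit, not an analysis schedule. At two-week cycles, cycle 56 starts 55 x 2 = 110 weeks after baseline. Section 9.2.1 leaves the last patients enrolled about 52 weeks, roughly 26 cycles, and only about half of all patients are expected to complete questionnaires throughout. Late tests would be sparse.
- The counts assume no true change. Section 7.2 itself expects adverse events to affect quality of life, and 7.1 reports skin events in more than 90% of panitumumab patients.
- A reader might argue that a total would add scales pointing in opposite directions. Section 9.3.2 gives no scoring direction for the QLQ-C30, and the total may simply mean the global health status scale. The documents support asking for a definition, no more.
- The schedule wording in 9.1 may have meant each subsequent cycle, which would agree with Table 1. It is ambiguous, it can change the number of tests twofold, and it is a separate matter from the inference problem.

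**Conclusion.** The concern holds. Section 7.3 contradicts the abstract, 9.7.2.1 and 9.7.2.4, and the tests attached to the primary endpoint have no primary scale, primary time, defined total or multiplicity control. This follows from the text alone.

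The size is conditional: from a handful to dozens of chance results, depending on how many times and comparisons are tested. The figures in the table rest on the full grid of 14 scores and on no true change anywhere. They show scale and do not predict the study's results. That the plan does not allow the number of tests to be fixed is part of the defect.

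**What to change.** **Preferred: make the analysis match Section 7.3.** Delete the 0.05 sentence and the t-test wording in the abstract, 9.7.2.1 and 9.7.2.4. Report mean changes from baseline and between-drug differences as estimates with 95% confidence intervals and no p-values. State that the intervals are unadjusted and are not to be read as tests, since otherwise the same multiplicity returns through intervals that exclude zero.

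**Alternative, if the sponsor wants a test.** Amend 7.3 and the abstract. Pre-name one QLQ-C30 scale, for example global health status/QoL, at one fixed assessment with a visit window, as the only contrast tested at 0.05. Report everything else as estimates with confidence intervals. The window matters because visits follow cycles and the plan expects delayed cycles. The choice of scale and time is the sponsor's; the documents do not dictate it.

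**In either case.** Define the total score, for example as the global health status scale, or remove it. Reconcile the questionnaire timing in 9.1 with the study visits in 9.3 and Table 1.

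**Cost.** Changes to protocol and SAP wording only, with no new patients or data. The downside is that fewer results can be called significant.

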## 8. Research Question and Objectives

### 8.1 Primary

To assess the impact of the treatment with FOLFOX or FOLFIRI plus anti-EGFR MAb on patients' health related quality of life (HRQoL), as measured by means of the EORTC – QLQC30 questionnaire.

Approved

## 8.2 Secondary

To investigate the impact of dermatological adverse events during the treatment with FOLFOX or FOLFIRI plus anti-EGFR MAbs on patients' skin satisfaction as measured by means of the Dermatology Life Quality Index (DLQI) questionnaire.

To assess the tolerability of administered treatments.

To describe the adherence to the treatment in terms of dose delays, dose reductions, number of administered cycles, average relative dose intensity of every drug.

To describe the management of dermatological adverse events.

To assess the effect on skin-related QoL of preemptive vs reactive treatment of skin toxicities.

## 9. Research Methods

### 9.1 Study Design

This is a national, multicentric, prospective, observational trial. The decision to prescribe FOLFOX or FOLFIRI plus panitumumab or FOLFOX or FOLFIRI plus cetuximab must have been freely taken by the clinician prior to the study entry for each patient included. Each physician will see his/her patients within the context of routine visits, without any special visit being organized for the purposes of the study. Therefore, the doctor-patient relationship and patient follow-up are not modified. Physicians are totally free to decide on their patients' therapeutic management.

EORTC QLQ-C30 and DLQI questionnaires will be completed by the patients at baseline (Day 1 of Cycle 1), at the first day of every other cycle (every 2 weeks) thereafter, and at "End of Study Visit" (within 28 days from the end of treatment with anti-EGFR or withdrawal from study for any reason).

Before every cycle, adverse events will be recorded and graded according to NCI CTCAE Version 4.0. Treatment's modifications in terms of cycles' delay, dose reductions or drugs' interruptions will be recorded. Concomitant approaches to prevent or treat dermatological toxicities during the treatment will be registered.

### 9.2 Setting and Study Population

#### 9.2.1 Study Period

Around **50** months to enroll 300 patients

Patient's enrollment will start approximately in November 2015 and will end approximately in **December 2019**. The end of study is planned for **December 2020**.

## 9.2.2 Selection and Number of Sites

Around 33 Italian Oncology Centers will participate to the study.

## 9.2.3 Subject/Patient/Healthcare Professional Eligibility

### 9.2.3.1 Inclusion Criteria

Adult ( $\geq$  18 years old) RAS wild-type metastatic colorectal cancer patients candidate to receive FOLFOX or FOLFIRI plus panitumumab or FOLFOX or FOLFIRI plus cetuximab as upfront treatment as per clinical practice.

Willingness and ability to comply with the protocol.

Written informed consent to study procedures.

